5.2 Secondary Objectives

Secondary objectives will assess POP-Q Stage and patient satisfaction at 6 weeks, 6 months, 2 years, and 3 years post implant, as follows:

Change in prolapse stage from baseline as determined objectively by POP-Q prolapse grading at 6 weeks, 6 months, 2 year, and 3 year follow-ups. Change in patient satisfaction from baseline and quality of life measured through validated questionnaires (PDFI-20 and PFIQ-7)⁶

Change in patient sexual satisfaction from baseline measured through a validated questionnaire (PISQ-12)⁷

Summary of Patient Global Impression of Improvement (PGI-I) for urogenital prolapse⁹ results

Summary of The Institute for Female Pelvic Medicine & Reconstructive Surgery Surgical Satisfaction Questionnaire (SSQ-8) results¹⁰

Change in Pelvic and Sexual Health Institute Visual Analog Scale (VAS)¹¹ results

Surgical revision rate of the index prolapse(s)

Summary of all mild, moderate, and serious product and/or procedure related adverse events

6 Study Population

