8.4 Follow-Up Schedule

Follow-up visits are required at 6 weeks, 6 months, 1 year, 2 years, and 3 years post implant. If the participant misses any required follow-ups, a Study Deviation Form must be completed. Every attempt should be made to complete the visit, however, if the subject cannot be seen in person the required questionnaires should be mailed to the participant with a postage paid return envelope. If a scheduled visit is not within the follow-up window, the visit should still be completed as soon as possible and a Study Deviation Form completed.

Table 2 Follow-up Schedule & Visit Windows

Follow-Up	Window Start	Target Day	Window End
[REDACTED]	[REDACTED]	[REDACTED]	[REDACTED]
[REDACTED]	[REDACTED]	[REDACTED]	[REDACTED]
[REDACTED] [REDACTED]	[REDACTED]	[REDACTED]	[REDACTED]
[REDACTED] [REDACTED]	[REDACTED]	[REDACTED]	[REDACTED]

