Appendix B: Patient Questionnaires

Patient Global Impression of Improvement for Urogenital Prolapse (PGI-I for Urogenital Prolapse)

Subject ID: _____ - _____

Visit Date: ____/____/____
MM/DD/YYYY

1. Check the box that best describes how your urinary tract condition is now, compared with how it was before you had the operation.

¹Very much better ²Much better ³A little better ⁴No change

⁵A little worse ⁶Much worse ⁷Very much worse

Reference:

**Pelvic Floor Distress Inventory –
Short Form 20**

Subject ID: _____ - _____
Visit Date: ____/____/____ MM/DD/YYYY

Instructions:

Please answer the questions by putting an X in the appropriate box. If you are unsure about how to answer a question, give the best answer you can. While answering these questions, please consider your symptoms over the last 3 months. CHECK ONE BOX PER QUESTION. Thank you for your help.*

1. Do you usually experience *pressure* in the lower abdomen? No Yes
If yes, how much does this bother you?
₁ Not at all ₂ Sometimes ₃ Moderately ₄ Quite a bit
◇ ◇ ◇ ◇ ◇ ◇
2. Do you usually experience *heaviness* or *dullness* in the pelvic area? No Yes
If yes, how much does this bother you?
₁ Not at all ₂ Sometimes ₃ Moderately ₄ Quite a bit
◇ ◇ ◇ ◇ ◇ ◇
3. Do you usually have a bulge or something falling out that you can see or feel in the vaginal area? No Yes
If yes, how much does this bother you?
₁ Not at all ₂ Sometimes ₃ Moderately ₄ Quite a bit
◇ ◇ ◇ ◇ ◇ ◇
4. Do you usually have to push on the vagina or around the rectum to have a complete bowel movement? No Yes
If yes, how much does this bother you?
₁ Not at all ₂ Sometimes ₃ Moderately ₄ Quite a bit
◇ ◇ ◇ ◇ ◇ ◇
5. Do you usually experience a feeling of incomplete bladder emptying? No Yes
If yes, how much does this bother you?
₁ Not at all ₂ Sometimes ₃ Moderately ₄ Quite a bit
◇ ◇ ◇ ◇ ◇ ◇
6. Do you ever have to push up on a budge in the vaginal area with your fingers to start or complete urination? No Yes
If yes, how much does this bother you?
₁ Not at all ₂ Sometimes ₃ Moderately ₄ Quite a bit

Subject ID: _____ - _____
Visit Date: ____/____/____ MM/DD/YYYY

- 14. Does a part of your bowel ever pass through the rectum and bulge outside during or after a bowel movement?
If yes, how much does this bother you?
₀ No Yes
₁ Not at all ₂ Sometimes ₃ Moderately ₄ Quite a bit
◇◇◇◇◇◇

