- 15. Do you usually experience frequent urination?
If yes, how much does this bother you?
₀ No Yes
₁ Not at all ₂ Sometimes ₃ Moderately ₄ Quite a bit
◇◇◇◇◇◇
- 16. Do you usually experience urine leakage associated with a feeling of urgency, that is a strong sensation of needing to go to the bathroom?
If yes, how much does this bother you?
₀ No Yes
₁ Not at all ₂ Sometimes ₃ Moderately ₄ Quite a bit
◇◇◇◇◇◇
- 17. Do you usually experience urine leakage related to coughing, sneezing, or laughing?
If yes, how much does this bother you?
₀ No Yes
₁ Not at all ₂ Sometimes ₃ Moderately ₄ Quite a bit
◇◇◇◇◇◇
- 18. Do you usually experience small amounts of urine leakage (that is drops)?
If yes, how much does this bother you?
₀ No Yes
₁ Not at all ₂ Sometimes ₃ Moderately ₄ Quite a bit
◇◇◇◇◇◇
- 19. Do you usually experience difficulty emptying your bladder?
If yes, how much does this bother you?
₀ No Yes
₁ Not at all ₂ Sometimes ₃ Moderately ₄ Quite a bit
◇◇◇◇◇◇
- 20. Do you usually experience *pain* or *discomfort* in the lower abdomen or genital region?
If yes, how much does this bother you?
₀ No Yes
₁ Not at all ₂ Sometimes ₃ Moderately ₄ Quite a bit

Subject ID: _____
Visit Date: ____/____/____ MM/DD/YYYY

Pelvic Floor Impact Questionnaire – short form 7

Instructions: Some women find that bladder, bowel or vaginal symptoms affect their activities, relationships, and feelings. For each question, place an X in the response that best describes how much your activities, relationships, and feelings have been affected by your bladder, bowel, or vaginal symptoms or conditions over the last 3 months. Please be sure to mark an answer in **all three columns** for each question. Thank you for your cooperation.*

How do symptoms or conditions related to the following usually affect your... ↓	Bladder or urine	Bowel or rectum	Vagina or Pelvis
1. ability to do household chores (cooking, housecleaning, laundry)?	 Not at all  Somewhat  Moderately  Quite a bit	 Not at all  Somewhat  Moderately  Quite a bit	 Not at all  Somewhat  Moderately  Quite a bit

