7. feeling frustrated?	 Not at all  Somewhat  Moderately  Quite a bit	 Not at all  Somewhat  Moderately  Quite a bit	 Not at all  Somewhat  Moderately  Quite a bit

Subject ID: _____ - _____
Visit Date: ____/____/____ MM/DD/YYYY

Pelvic Organ Prolapse / Urinary Incontinence Sexual Function Questionnaire (PISQ-12)

Instructions: The following are a list of questions about you and your partner's sex life. All information is strictly confidential. Your confidential answers will be used only to help doctors understand what is important to patients about their sex lives. Please check the box that best answers the question for you. While answering the questions, consider your sexuality over the last 6 months. CHECK ONE BOX PER QUESTION. Thank you for your help.*

I am not sexually active or I am not comfortable answering these questions (do not answer the questions below).

1. How frequently do you feel sexual desire? This feeling may include wanting to have sex, planning to have sex, feeling frustrated due to lack of sex, etc.

Always Usually Sometimes Seldom Never

2. Do you climax (have an orgasm) when having sexual intercourse with your partner?

Always Usually Sometimes Seldom Never

3. Do you feel sexually excited (turned on) when having sexual activity with your partner?

Always Usually Sometimes Seldom Never

4. How satisfied are you with the variety of sexual activities in your current sex life?

Always Usually Sometimes Seldom Never

5. Do you feel pain during sexual intercourse?

Always Usually Sometimes Seldom Never

6. Are you incontinent of urine (leak urine) with sexual activity?

Always Usually Sometimes Seldom Never

7. Does fear of incontinence (either stool or urine) restrict your sexual activity?

Always Usually Sometimes Seldom Never

8. Do you avoid sexual intercourse because of bulging in the vagina (either bladder, rectum, or vagina falling out)?

Always Usually Sometimes Seldom Never

9. When you have sex with your partner, do you have negative emotional reactions such as fear, disgust, shame or guilt?

Always Usually Sometimes Seldom Never

Subject ID: _____ - _____
Visit Date: ____/____/____ MM/DD/YYYY

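### At 6 weeks the PFDI-20, PFIQ-7 and PISQ-12 recall windows reach back before surgery, so the 6-week change from baseline may mix the untreated and treated periods

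*Combined protocol and SAP*

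**What the plan says.** Section 5.2 opens with: "Secondary objectives will assess POP-Q Stage and patient satisfaction at 6 weeks, 6 months, 2 years, and 3 years post implant, as follows". Two of the items listed beneath it are "Change in patient satisfaction from baseline and quality of life measured through validated questionnaires (PDFI-20 and PFIQ-7") and "Change in patient sexual satisfaction from baseline measured through a validated questionnaire (PISQ-12"). The first misprints PFDI-20. Neither item names its own time points, so both take them from the lead sentence. Section 8.4 confirms an early visit: "Follow-up visits are required at 6 weeks, 6 months, 1 year, 2 years, and 3 years post implant".

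The forms in Appendix B fix the recall period:

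- PFDI-20: "While answering these questions, please consider your symptoms over the last 3 months".
- PFIQ-7: "bladder, bowel, or vaginal symptoms or conditions over the last 3 months".
- PISQ-12: "While answering the questions, consider your sexuality over the last 6 months".

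Under section 8.2, the baseline forms must be completed within a 6-month limit around the implant procedure. The readable text contains no 6-week version of these forms, no instruction to answer for the time since surgery, and no rule for handling the 6-week scores. Table 1 and the content of section 8.5 are not readable, the visit windows in Table 2 are redacted, and parts of section 14 are redacted.

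**The concern.** A woman who follows the printed instruction at 6 weeks has to look back past the operation. Her answer then covers some weeks of untreated prolapse, the operation, early recovery and a short treated period. Her baseline answer covers untreated prolapse only. The difference between the two is meant to describe the effect of the repair, but part of it compares one untreated period with another.

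Two results could mislead. The 6-week change may look smaller than the benefit at that time. The score may then appear to go on improving up to 6 months only because the untreated weeks have dropped out of the window, and this could be read as progressive benefit from the graft. The study has a single arm, so no control group would expose the artefact.

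**Working it through.** The plan gives no figure on this point, so there is none to reproduce. The check is date arithmetic.

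**Inputs.** Recall length W is 3 months (PFDI-20, PFIQ-7) or 6 months (PISQ-12), from Appendix B. The visit target is 6 weeks, d = 42 days, from sections 5.2 and 8.4. One month is taken as 365.25/12 = 30.44 days, so W = 91.3 or 182.6 days. The actual visit day is an assumption, because the windows are redacted.

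**Share of the window before surgery** = (W − d)/W.

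- 3-month forms: (91.3 − 42)/91.3 = 49.3/91.3 = 54%.
- PISQ-12: (182.6 − 42)/182.6 = 140.6/182.6 = 77%.

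With 30-day months the shares are 53% and 77%. With 28-day months they are 50% and 75%.

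**Sensitivity to the visit day (30.44-day months).**

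| Visit day | PFDI-20, PFIQ-7 | PISQ-12 |
|---|---|---|
| 35 | 62% | 81% |
| 42 | 54% | 77% |
| 45 | 51% | 75% |
| 49 | 46% | 73% |
| 56 | 39% | 69% |

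The share equals one half at d = W/2, which is day 45.7 for the 3-month forms and day 91.3 for PISQ-12. For the 3-month forms, some overlap with the pre-operative period remains at any visit before about day 91.

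**Overlap with the baseline window.** If baseline is completed on the day of surgery, the two windows share the same 49 days (3-month forms) or 141 days (PISQ-12). An earlier baseline shares fewer days, but the pre-operative part of the 6-week window is still untreated time.

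**Illustration of the effect on the score.** Assume that the answer is an even time average over the window, that the pre-operative state is stable, and that benefit is immediate and constant. Then observed change = (d/W) × true change.

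- 3-month forms: 42/91.3 = 46% of the true change, an attenuation of 54%.
- PISQ-12: 42/182.6 = 23% of the true change, an attenuation of 77%.

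At the 6-month target (day 183) neither window reaches back before surgery, so the full change appears. The apparent gain from 6 weeks to 6 months would be 54% or 77% of the true change with no real change in that interval. If women instead report their current state, attenuation is 0.

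**Six-month visit, PISQ-12.** Pre-operative share is 0% at day 183, (182.6 − 168)/182.6 = 8% at day 168, and (182.6 − 152)/182.6 = 17% at day 152. For the 3-month forms it is 0% on all three days.

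**The case against.** **Six-week use of the forms is inferred.** The tables and text that would show which form is given at which visit cannot be read, and Table 1 may hold some forms back until later; PISQ-12, which only sexually active women complete, is the least certain. An analysis rule for 6-week scores could also sit in redacted text. This stands as a limit on certainty, and silence in redacted text is not a fault of the plan. But the lead sentence of section 5.2 does cover these items at 6 weeks, and if the schedule says otherwise, that sentence still needs correcting.

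**Women may not average over the window.** The PFDI-20 and PFIQ-7 items are in the present tense and ask what is usual. Item 12 of PISQ-12 refers to the time since the previous study visit, so that form does not apply one window throughout. This stands: a reader might infer that the 6-week scores certainly understate benefit or cannot be used at all, and the documents support neither. The window also contains the operation and recovery, whose effect on the scores is not known.

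**Most of the window is pre-operative only at or near target.** A reader might take this as true of all three forms. It is secure for PISQ-12. For the 3-month forms it is a narrow majority that fails after about day 45. The substance does not depend on a majority.

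**The 6-month PISQ-12.** It is tempting to set this visit aside as well and start at 1 year. At the 6-month target there is no pre-operative carry-over, so the recall argument does not require it, and the lead sentence of section 5.2 does not list 1 year.

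**Little depends on it.** Section 14.1 states that there are no predefined hypotheses, and no test or decision in the readable text uses the 6-week scores. This is correct, and it limits the weight of the point without removing it.

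**Conclusion.** The point holds in a limited form. As printed, the forms ask about a period that, at the 6-week target, lies about 54% (PFDI-20, PFIQ-7) or 77% (PISQ-12) before surgery. The 6-week change from baseline may therefore understate early benefit and may create an apparent further improvement by 6 months. The attenuation lies between 0 and about 54% or 77%; the upper ends hold at day 42 under the illustrative even time average with an immediate, constant effect, and the documents do not show where in that range the truth lies.

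The conclusion rests on reading section 5.2 as applying 6 weeks to all three forms, and on visits falling near day 42. Only an early secondary time point is affected. The primary endpoint, POP-Q stage at 1 year, is not, and neither are the 2- and 3-year questionnaire scores.

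**What to change.** In section 5.2, remove 6 weeks as a change-from-baseline time point for PFDI-20, PFIQ-7 and PISQ-12, and make 6 months the first. Note there that the 6-month PISQ-12 window includes operative recovery and can reach back before surgery if the visit is early.

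If the three forms are still collected at 6 weeks, report those scores descriptively, state the recall overlap beside them, and leave them out of any trend over time. This can still be done at reporting if the data have already been collected.

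Keep PGI-I, SSQ-8 and the VAS at 6 weeks if they are scheduled there; none of them prints a 3- or 6-month recall period. Check Table 1 against the revised wording.

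A recall instruction limited to the time since surgery is an alternative, but it departs from the forms as printed.

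The cost is a change of wording, with no effect on sample size, and the loss of an early change score that is hard to interpret.

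### Every visible PFDI-20 item asks for a degree of bother but labels code 2 with the frequency word *Sometimes*; check the form against its source questionnaire before use

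*Combined protocol and SAP*

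**What the plan says.** Section 5.2 (Secondary Objectives) includes change from baseline in satisfaction and "quality of life measured through validated questionnaires (PDFI-20 and PFIQ-7"; the first acronym is printed with two letters transposed, and section 8.2 lists the same instrument as the PFDI-20. Section 14 counts the subject questionnaires among the efficacy metrics. Section 14.2 plans a comparison of results with competing products in the literature, without saying which results.

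In the PFDI-20 form in Appendix B, each item first asks whether a symptom occurs and then asks "If yes, how much does this bother you". The answers offered are "Not at all ₂ Sometimes ₃ Moderately", followed by *Quite a bit* as code 4.

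Two other forms in the appendix help in reading that scale. The PFIQ-7 has the same first, third and fourth labels, but its second and third read "Somewhat Moderately". The PISQ-12 runs "Always Usually Sometimes Seldom Never", where *Sometimes* is plainly a frequency.

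**The concern.** The follow-up question asks for an amount of bother, and one of its four answers gives a frequency. A woman who is slightly but constantly bothered may not recognise herself in *Sometimes*. A woman who is rarely but badly bothered could tick either that box or a higher one. The first part of each item already asks whether the symptom is usually or ever present, so a frequency word in the second part mixes two ideas.

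This is the answer scale for a named secondary outcome, so the wording bears on the data themselves. The study has one arm, so no concurrent control group answers the same wording, and any comparison between products has to come from outside the study. Section 8.4 has questionnaires mailed to women who cannot be seen in person, and the visible text does not say who would help them with an unclear label. If the printed form differs from the published one, describing it as validated and setting its scores beside published values would both need a caveat.

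**Working it through.** The plan states no figure on this point, so there is none to reproduce. The check is a reading of the labels side by side.

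1. **Count.** The readable PFDI-20 items are 1–6 (6 items), 14 (1 item) and 15–20 (6 items): 6 + 1 + 6 = 13. Items 7–13, the other 20 − 13 = 7, are not in the text available to this review. That is not a fault of the plan. Code 2 is *Sometimes* in 13 of 13 readable items, so a one-off reading error is unlikely.

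2. **Second label on the three forms.**

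| Form (Appendix B) | What is asked | Label in question | Kind of word |
|---|---|---|---|
| PFDI-20, 13 readable items | Amount of bother | *Sometimes*, between *Not at all* and *Moderately* | Frequency |
| PFIQ-7, all 7 items | Effect on activities and feelings | *Somewhat*, between *Not at all* and *Moderately* | Degree |
| PISQ-12, items 1–11 | Mostly how often | *Sometimes*, between *Usually* and *Seldom* | Frequency |

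The PFDI-20 and PFIQ-7 scales share three of four labels and differ only in the second. Within this appendix, the PFDI-20 word belongs to the kind of scale used in the PISQ-12.

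3. **Sign of retyping.** Item 6 of the PFDI-20 reads "Do you ever have to push up on a budge in the vaginal area", where item 3 has the intended noun, *bulge*. This suggests a form that was retyped without a full proofread. It does not prove that the label was changed.

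4. **What a size would need.** An item is scored 0 (No) to 4, so one category is 1 point, or 1/4 = 25% of the item range. The shift in the mean item score would be:

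   (share of items answered Yes) × (net share of those answers moved up or down one category) × 1 point

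   The documents give neither share. If 10–30% of Yes answers moved, all in one direction, and every item were answered Yes, the shift would be 0.1–0.3 points. If half the items were answered Yes, it would be 0.5 × 0.1 = 0.05 to 0.5 × 0.3 = 0.15. If moves up and down cancelled, it would be zero. All these shares are assumptions, so the range illustrates the arithmetic and does not estimate an effect.

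**The case against.** The strongest reply is that the published PFDI-20 is not in the documents. If it prints *Sometimes*, the form is faithful and nothing follows about validation or published scores. The PFIQ-7 is a different questionnaire with a different question, so its wording cannot settle what the PFDI-20 should say. This stands, and it limits the point to an ambiguity within the appendix that calls for a source check.

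Three stronger readings are tempting.

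- A reader might infer that the answers no longer form an ordered scale. The documents do not show that. The boxes are numbered 1 to 4, the label sits between two degree words under a question about amount, and many women may read it by position. The label is ambiguous; loss of order is not established.
- A reader might infer that the planned literature comparison will use these scores. Section 14.2 does not name the PFDI-20, and the text just before that sentence is redacted. Such a comparison is possible, and it could be affected.
- A reader might infer that the faulty label appears in all 20 items and at every visit. Items 7–13 and the detailed content of the follow-up visits cannot be seen; only baseline use is itemised.

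It is also fair to say that the same form at each visit gives change from baseline some protection. That protection is partial: it relies on women reading the label in the same way before and after surgery, and surgery may alter how often and how much a symptom bothers them to different extents. It does nothing for a comparison with published scores.

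**Conclusion.** The point holds in limited form. All 13 readable PFDI-20 items pair a question about amount with a frequency word at code 2, and the appendix itself shows the contrast. The result is an avoidable ambiguity in a secondary outcome described as validated. No size can be derived from the documents. The primary POP-Q endpoint does not depend on this form, and the sample size rests on the precision of estimates with no predefined hypotheses, so neither changes.

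The conclusion assumes that the readable items are printed as shown. Whether the form departs from the published instrument remains open until the source is checked; if it does not depart, the statement that it is validated is unaffected by this point. The correction is worth making before use because it is cheap then, whereas answers already given cannot be repaired.

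**What to change.** - **Before the form is used:** check all 20 PFDI-20 items, including 7–13, against the questionnaire cited in section 5.2. If the source has the degree word, replace *Sometimes* with *Somewhat* on the form and in the eCRF. Codes and scoring stay as they are. If the source itself prints *Sometimes*, leave the label, since changing it would create the departure it was meant to remove.
- **If women have already answered the present form and it differs from the source:** keep each of them on the same version for all visits, so that a change of wording does not enter her change from baseline. Record the version with each questionnaire and report the wording as a limitation. Do not describe the altered form as validated, or compare its scores with published values, without that caveat.
- **Cost:** one reprint, an eCRF label update and an IRB submission of the corrected form at each site. Section 16.2 sends amendments that affect study conduct back to the same local IRB; with the planned 5 to 10 sites, that is 5 to 10 submissions if each site has its own board.

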8.1 Data Collection Schedule

8.2 Baseline

The following will be collected at baseline:

Consent Form Obtained

The signed and dated consent form will be obtained prior to any study information being collected at the Baseline Visit.

Entrance Criteria Verified

The inclusion/exclusion criteria will be verified at the Baseline Visit.

Demographics, Medical History

Participant demographics, medical history related to pelvic organ prolapse, and other relevant medical history will be collected.

Subject evaluation/examination required within 6 months of the implant procedure

Objective POP-Q prolapse grading [REDACTED]

Clinical exam

Other Symptoms

Urinary symptoms

Colo-rectal symptoms

Incontinence measures, if applicable and standard of care (Uroflowmetry, Cystoscopy)

Participant Questionnaires required within 6 months of the implant procedure.

Pelvic Floor Distress Inventory Short Form (PFDI-20)

Pelvic Organ Prolapse/ Urinary Incontinence Sexual Function Questionnaire (PISQ-12) [for sexually active subjects]

Pelvic Floor Impact Questionnaire Short Form (PFIQ-7)

Pelvic and Sexual Health Institute Visual Analog Scale (VAS)

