Pelvic Organ Prolapse / Urinary Incontinence Sexual Function Questionnaire (PISQ-12)

10. Does your partner have a problem with erections that affects your sexual activity?
 Always Usually Sometimes Seldom Never
11. Does your partner have a problem with premature ejaculation that affects your sexual activity?
 Always Usually Sometimes Seldom Never
12. Compared to orgasms you have had in the past, how intense are the orgasms you have had since your last study visit?
 Much less intense Less intense Same intensity More intense Much more intense

Date: ____/____/____

Name: _____

Surgical Satisfaction Questionnaire SSQ-8

Instructions: Following are a list of questions about your satisfaction with your surgery. All information is strictly confidential. Your confidential answers will be used only to help doctors understand and improve what is important to patients before, during and after surgery. Please check the box that best answers the question for you. Thank you for your help.

- 1. How satisfied are you with how your pain was controlled in the hospital after surgery?
 Very Satisfied Satisfied Neutral Unsatisfied Very unsatisfied
- 2. How satisfied are you with how your pain was controlled when you returned home after surgery?
 Very Satisfied Satisfied Neutral Unsatisfied Very unsatisfied
- 3. How satisfied are you with the amount of time it took for you to return to your daily activities, for example housework or social activities outside the home?
 Very Satisfied Satisfied Neutral Unsatisfied Very unsatisfied
- 4. How satisfied are you with the amount of time it took for you to return to work?
 Very Satisfied Satisfied Neutral Unsatisfied Very unsatisfied N/A
- 5. How satisfied are you with the amount of time it took for you to return to your normal exercise routine?
 Very Satisfied Satisfied Neutral Unsatisfied Very unsatisfied N/A
- 6. How satisfied are you with the results for your surgery?
 Very Satisfied Satisfied Neutral Unsatisfied Very unsatisfied
- 7. Looking back, if you "had to do it all over again" would you have the surgery again?
 Yes Maybe (probably yes) Unsure Don't think so Never
- 8. Would you recommend this surgery to someone else?
 Yes Maybe (probably yes) Unsure Don't think so Never

NOTES: Research Nurses Notes

Originated 08/08

Subject ID#: _____ Date: _____ Visit: (Circle) Pre-Op 1 2 3 4 5

Indicate pain on the line below, with one vertical mark
Do not write a number

Pelvic/Bladder Pain with Daily Activity

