No Pain	_____	Worst Pain
---------	-------	------------

Pelvic/Bladder Pain with Sexual Activity

No Pain	_____	Worst Pain
---------	-------	------------

Comments:

To obtain "final" score use a 10-cm measurement tool/ruler, clinician can note precise VAS score to the tenths decimal place (e.g. 8.2 cm, 3.1 cm).

Final VAS score: _____ (Daily Activity); _____ (Sexual Activity)

VAS Entered into Database by/Date: _____ PI Review/Date: _____

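### The VAS line for pain with sexual activity has no not-applicable choice, and the merged PISQ-12 opt-out box cannot show who was inactive or who stopped because of pain

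*Combined protocol and SAP*

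**What the plan says.** Section 5.2 lists two relevant secondary objectives. One is "Change in patient sexual satisfaction from baseline measured through a validated questionnaire (PISQ-12"); the other is change in the Pelvic and Sexual Health Institute VAS.

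The VAS form in Appendix B has two lines, one for daily activity and one headed "Pelvic/Bladder Pain with Sexual Activity". The instruction is "Indicate pain on the line below, with one vertical mark". Each line runs from no pain to worst pain and is measured with a 10-cm ruler. The score fields read "Final VAS score: _____ (Daily Activity); _____ (Sexual Activity"). Apart from these there is a free-text comments space and a sign-off field. The form has no not-applicable choice, no activity status and no field for a reason.

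The PISQ-12 in Appendix B opens with one box: "I am not sexually active or I am not comfortable answering these questions (do not answer the questions below"). A woman who ticks it skips every item, including item 5 on pain during intercourse.

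Section 8.2 lists the PISQ-12 as "for sexually active subjects". The VAS stands in the same list without that limit.

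**The concern.** Pain with sexual activity is a harm that a study of a vaginal graft should be able to see, and two secondary endpoints bear on it. On the VAS, a woman who is not sexually active has no valid answer. A mark at the left end is stored as 0 cm and looks like a pain-free active woman. A blank could mean inactivity, reluctance or oversight. On the PISQ-12, a woman who has stopped and ticks the box gives no follow-up score, and so no change score. In the data she looks the same as a woman who is inactive for another reason, or who is active and prefers privacy.

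The woman who stopped because of pain matters most here. She may enter the VAS change as a 0, or drop out of both change scores, and no structured field records why.

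**Working it through.** **Reading the forms together**

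- The packet does offer a not-applicable choice elsewhere: SSQ-8 items 4 and 5 print one. The VAS line does not.
- PISQ-12 item 7 concerns restriction from fear of incontinence and item 8 avoidance because of bulging. No item asks about avoidance because of pain, and all items sit behind the opt-out box.
- Under section 8.4, questionnaires are mailed when a woman cannot be seen in person, so no staff member is then present to clarify the line.

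**Inputs**

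The plan gives no figure on this point to reproduce. The only related one is 60 to 85 evaluable subjects at month 12 (section 14.1). The following inputs are assumptions:

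- q: share of women active at baseline who stop because of pain, 5 to 10%.
- T: the pain that those women would score at follow-up, 7 cm.
- C: mean follow-up pain of women who continue, 2 cm.
- B: baseline mean, 3 cm, the same in stoppers and continuers.

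**Formulas for mean change among women active at baseline**

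- True: (1 − q)(C − B) + q(T − B).
- Stoppers mark 0: (1 − q)(C − B) + q(0 − B). Subtracting the true value gives a bias of −qT.
- Stoppers left blank: C − B. Subtracting the true value gives a bias of −q(T − C).

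| q | True | Stoppers at 0 | Stoppers left out | Bias if 0 | Bias if left out |
|---|---|---|---|---|---|
| 5% | −0.75 | −1.10 | −1.00 | −0.05 × 7 = −0.35 | −0.05 × 5 = −0.25 |
| 10% | −0.50 | −1.20 | −1.00 | −0.10 × 7 = −0.70 | −0.10 × 5 = −0.50 |

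All changes are in cm; negative means less pain. T is follow-up pain and B cancels from −qT, so that result also covers new pain. A woman who starts near 0, stops and marks 0 contributes no change where she should contribute a worsening. The left-out result does need equal baseline means.

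Over T = 4 to 9 cm and q = 5 to 20%, with C = 2 cm, the bias runs from −0.20 to −1.80 cm if scored 0 and from −0.10 to −1.40 cm if left out.

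**How few women decide it**

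If 40 to 60% are sexually active (assumed), 24 to 36 of 60 or 34 to 51 of 85 contribute. At q = 5 to 10% the stoppers number from 24 × 0.05 = 1.2 to 51 × 0.10 = 5.1, or about 1 to 5 women.

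**Women inactive at both visits**

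If a share r of all women mark 0 both times, a change D among active women shows as D(1 − r). With r = 30 to 50% (assumed), a 2.0 cm change in either direction shows as 2.0 × 0.7 = 1.4 to 2.0 × 0.5 = 1.0 cm. This is dilution, not bias towards benefit. A woman who marks 0 while inactive at baseline and later resumes could even show a false worsening.

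**The case against.** Nothing tells an inactive woman to mark the left end. She may leave the line blank or explain herself in the comments, and the form has a review field. That stands: a false zero is possible, not certain.

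Most of section 14.2 is redacted, and the data collection table and follow-up visit content are not shown, so a scoring or eligibility rule may exist. A reader might infer that the plan has none; the visible text does not support that. A rule could settle how blanks are handled. It could not recover a reason that the printed forms do not collect in a structured field.

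A reader might also infer that new pain would go undetected. PFDI-20 item 20 asks every woman about pain or discomfort in the lower abdomen or genital region. The VAS has a daily-activity line, and related adverse events of all grades are a secondary objective. These sources give partial capture, though they may miss pain felt only with intercourse. They do not correct the VAS or PISQ-12 change scores.

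Finally, limiting a sexual-function score to sexually active women is a conventional and openly stated choice. That is fair, and the point does not dispute it. The difficulty is that activity status is not cleanly recorded.

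**Conclusion.** The point holds for these two forms. The sexual-activity VAS can mix false zeros and uninterpretable blanks into a change endpoint, and the merged PISQ-12 box can neither sort them out nor identify women who stopped because of pain.

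Under the assumed q = 5 to 10%, T = 7 cm and C = 2 cm, the bias in mean VAS change is −0.35 to −0.70 cm if stoppers mark 0. It is −0.25 to −0.50 cm if they are left out and baseline means are equal. In both cases it runs towards apparent benefit when T exceeds C. The effect on the PISQ-12 is not quantified here.

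It would go too far to say that stopping because of pain is always recorded as 0 or missing, or that every inactive woman pushes the result towards benefit. The forms permit the first but do not dictate it, and women inactive throughout only dilute the change. The primary POP-Q endpoint is unaffected, so this is a worthwhile correction to secondary endpoints and not a flaw in the main result.

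**What to change.** - At every visit including Pre-Op, ask all women a separate status question: sexually active; not active because of pain; not active because of bulge or leakage; not active for another reason; prefer not to answer.
- Use a fixed recall period that works at baseline, such as current status. Asking about the time since the previous visit would have no meaning at Pre-Op. With later visits a year apart, it would also count a woman who stopped mid-interval as active.
- Add a box to the sexual-activity VAS line for women who are not currently sexually active. Code it as not applicable, never 0.
- Leave the PISQ-12 items unchanged.
- Beside the change scores in women active at both visits, report active/inactive transitions from baseline, including the number who stopped because of pain. Add a sensitivity analysis that counts those women as worsened.

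The cost is one question, one box, matching eCRF fields, one table and one sensitivity analysis; the form becomes slightly longer.
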